10.4.1. Rescue Therapy

A patient may be considered for rescue therapy treatment by the Investigator according to local practice (which may include corticosteroids or immunosuppressants) if the following conditions are met:

- It is recommended that the patient is in the study for over one year. However, rescue therapy may be administered at less than one year if clinically warranted
- Patient meets study eligibility criteria (other than eGFR ≥ 30), including 24-hour UPE > 1 g or 24-hour uPCR > 0.75 , twice over an 8-week period
- Patient has 100% increase in 24-hour UPE from baseline and patient has a 30% decrease in eGFR from baseline, as measured twice over an 8-week period
- Use of rescue therapy is discussed with the sponsor's medical monitor

The Investigator is encouraged to contact the sponsor Medical Monitor to discuss the use of rescue therapy, although it is not mandatory.

Rescue therapy for study patients is not encouraged given that there is no specific medication or treatment regimen approved for IgAN. However, if the Investigator feels that rescue therapy is required, and the patient meets the above criteria, the patient may be managed per local guidelines at the Investigator's discretion, however the patient must be withdrawn from study treatment. Patients requiring rescue treatment will be followed per protocol through the Follow-Up Period.

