Natural logarithm transformation will be used to analyze 24-hour UPE, 24-hour uPCR, 24-hour uACR, spot-urine uPCR and spot-urine uACR. Geometric-mean ratio relative to the study baseline will be presented by treatment group and visit for the FAS population. A repeated measures model for the change in the log-transformed value from baseline will be used for analysis. The model will include treatment, time (as a categorical variable for the scheduled timepoints), treatment by time interaction, randomization strata as fixed effects and a time-dependent covariate for open-label treatment of narsoplimab as fixed effects, and an AR (1) covariance matrix. The time-dependent covariate is a binary variable that has a value of 0 before the initiation of the open-label treatment and 1 afterwards. It is defined for the placebo group only. The REML method will be used to estimate the model parameters. The difference in least squares (LS) means between the treatment groups and its 95% CI will be estimated for each post-baseline scheduled visit. The LS mean will be estimated with 95% CI for each treatment group. The ratio of the GMR between the treatment groups will also be estimated with 95% CI. It is noted that the primary analysis of 24-hour UPE is based on the 24-hour UPE up to Week 36 and the time-dependent covariate is not applicable to the primary analysis.

Time adjusted AUC change from baseline in spot-urine uPCR through 36 weeks will be calculated as the AUC of the change from baseline in spot-urine uPCR divided by the time from

CONFIDENTIAL

No use, disclosure, or reproduction outside of Omeros without prior written authorization

baseline to the last observation on or before Week 36. Time average of change in spot-urine uPCR will be summarized descriptively. An ANOVA model with treatment and randomization strata as covariates will be performed.

The binary endpoints will be summarized descriptively. Non-responder imputation will be used to impute missing data. Exact 95% confidence intervals for the crude rate will be calculated and a CMH test stratified by the randomization stratum will be performed for the FAS population.

The time-to-event endpoints will be analyzed by Kaplan-Meier (KM) method for each treatment group for the FAS population. Median time with 95% confidence interval will be provided by treatment group. Log-rank test stratified by the randomization stratum will be performed.

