### Tertiary Endpoints

- Change from baseline in log-transformed 24-hour uPCR over time in patients in the high-risk proteinuria group (baseline 24-hour UPE  $\geq 2$  g/day)
- Achievement of  $\geq 50\%$  reduction from baseline in 24-hour UPE at 36 weeks in patients in the high-risk proteinuria group (baseline 24-hour UPE  $\geq 2$  g/day)
- Achievement of  $\geq 30\%$  reduction from baseline in 24-hour UPE at 36 weeks in patients in the high-risk proteinuria group (baseline 24-hour UPE  $\geq 2$  g/day)
- Change from baseline in log-transformed 24-hour uPCR over time in patients in the all-patients population (baseline 24-hour UPE  $> 1$  g/day)
- Achievement of  $\geq 50\%$  reduction from baseline in 24-hour UPE at 36 weeks in patients in the all-patients population (baseline 24-hour UPE  $> 1$  g/day)
- Achievement of  $\geq 30\%$  reduction from baseline in 24-hour UPE at 36 weeks in patients in the all-patients population (baseline 24-hour UPE  $> 1$  g/day)
- Time averaged change from baseline in the log-transformed 24-hour uPCR through 36 weeks in patients in the high-risk proteinuria group (baseline 24-hour UPE  $\geq 2$  g/day)
- Achievement of partial proteinuria remission defined as 24-hour UPE  $< 0.6$  g at any time post baseline in patients in the high-risk proteinuria group (baseline 24-hour UPE  $\geq 2$  g/day)
- Achievement of complete proteinuria remission defined as 24-hour UPE  $< 0.3$  g at any time post baseline in patients in the high-risk proteinuria group (baseline 24-hour UPE  $\geq 2$  g/day)
- Time averaged change from baseline in the log-transformed 24-hour uPCR through 36 weeks in patients in the all-patients population (baseline 24-hour UPE  $> 1$  g/day)

- Achievement of partial proteinuria remission defined as 24-hour UPE  $< 0.6$  g at any time post baseline in patients in the all-patients population (baseline 24-hour UPE  $> 1$  g/day)
- Achievement of complete proteinuria remission defined as 24-hour UPE  $< 0.3$  g at any time post baseline in patients in the all-patients population (baseline 24-hour UPE  $> 1$  g/day)
- Use of rescue therapy for IgAN at any time post baseline in patients in the all-patients population (baseline 24-hour UPE  $> 1$  g/day) and in patients in the high-risk proteinuria group (baseline 24-hour UPE  $\geq 2$  g/day)

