## 2.2. Analysis Populations

The primary efficacy analysis population will be the Full Analysis Set (FAS) population, defined as all randomized patients in the high-risk proteinuria group. Patients will be grouped by their assigned treatment. When considering the all-patients population (baseline 24-hour UPE  $> 1$  g/day), the same principal applies, i.e. the FAS for this population is defined as all randomized patients.

The supporting efficacy analysis populations will be the Per-Protocol Analysis Set population, which includes all randomized high-risk proteinuria patients who receive at least 10 doses of study drug in the Initial Treatment Period and have non-missing primary endpoint data (24-hour UPE at baseline and Week 36). Patients will be grouped by their assigned treatment.

Safety analyses will be based on the Safety Analysis Set, which includes all patients who receive any positive amount of study drug. Patients will be grouped by their actual treatment received. Supportive safety summaries will also be made in the population of all patients who receive any positive amount of study drug.

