#### 2.9.2.4. Other Efficacy Endpoints

All other efficacy endpoints will be analyzed for the FAS population.

Proteinuria durability will be evaluated by the time-adjusted AUC change from baseline in the log-transformed 24-hour UPE between 36 weeks and 48 weeks and between 36 weeks and 72 weeks. The time-adjusted AUC will be calculated as the AUC of the change in the log-transformed 24-hour UPE from baseline over the said time period divided by the time between the first observation and the last observation over the same said time period. All UPE values collected over the said time period, including values collected at unscheduled visits, will be used to calculate the time average. Patients who are on study and have not reached the Week 36 visit will be excluded from the analysis. The time-adjusted AUC will be summarized descriptively. Both the geometric-mean ratio relative to the study baseline and the coefficient of variation in percentage will be provided by treatment group for the FAS population. Multiple imputations with FCS regression method will be used to impute missing log-transformed 24-hour UPE at the scheduled visits from Week 12 to Week 72. The FCS regression method will include the treatment group and the randomization strata as covariates. The time-adjusted AUC will be calculated using the imputed values. The treatment difference will be estimated by an analysis of variance model with treatment and randomization strata as factors using the Rubin's rules with 20 imputations.

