Natural logarithm transformation will be used to analyze 24-hour UPE, 24-hour uPCR, 24-hour uACR, spot-urine uPCR, and spot-urine uACR. Geometric-mean ratio relative to the study baseline will be presented by treatment group and visit for the FAS population. A repeated measures model for the change in the log-transformed value from baseline will be used for analysis. The model will include treatment, time (as a categorical variable for the regular scheduled visits), treatment by time interaction, randomization strata as fixed effects, a time-dependent covariate for open-label treatment of narsoplimab as fixed effects, and an AR(1) covariance matrix. The time-dependent covariate is a binary variable that has a value of 0 before the initiation of the open-label treatment and 1 afterwards. It is defined for the placebo-treated group only. The REML method will be used to estimate the model parameters. The difference in LS means between the treatment groups and their respective 95% CIs will be estimated for each post-baseline scheduled visit. The LS mean will be estimated with 95% CI for each treatment group. The ratio of the GMR between the treatment groups will also be estimated with 95% CI. It is noted that the primary analysis of 24-hour UPE is based on the 24-hour UPE up to Week 36 and the time-dependent covariate is not applicable to the primary analysis.

Time-adjusted AUC change from baseline in log-transformed 24-hour uPCR through 36 weeks will be calculated as the AUC of the change from baseline in log-transformed 24-hour uPCR divided by the time from baseline to the last observation on or before Week 36. All 24-hour uPCR values collected from baseline to Week 36, including values collected at additional treatment visits and unscheduled visits, will be used to calculate the time adjusted AUC. Time

adjusted AUC of change in log-transformed 24-hour uPCR will be summarized descriptively. An analysis of covariance with treatment and randomization strata as factors and baseline uPCR as a covariate will be performed. The binary endpoints will be summarized descriptively. Non-responder imputation will be used to impute missing data. Exact 95% confidence intervals for the crude rate will be calculated and a Cochran–Mantel–Haenszel test stratified by the randomization stratum will be performed for the FAS population.

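### Use of rescue therapy falls under the non-responder imputation rule for binary endpoints, which has no clear meaning for an unfavourable event and leaves the scoring of patients who withdraw undefined

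*SAP*

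**What the plan says.** - **Endpoint.** The tertiary endpoints in SAP 2.1 include "Use of rescue therapy for IgAN at any time post baseline in patients in the all-patients population", and the same in the high-risk proteinuria group. Protocol 7.2.4 lists it under safety and other endpoints. Protocol 11.2 counts rescue use among the secondary efficacy measures.
- **Rule.** For the binary endpoints, SAP 2.9.2.4 states: "Non-responder imputation will be used to impute missing data. Exact 95% confidence intervals for the crude rate will be calculated", with a CMH test stratified by randomisation stratum. Protocol 14.1.10.3 agrees: "Non-responder imputation will be used to impute missing data". Neither text makes an exception.
- **Analysis set.** SAP 2.9.2.4: "All other efficacy endpoints will be analyzed for the FAS population". For the all-patients population, SAP 2.2 says "the FAS for this population is defined as all randomized patients". For the high-risk group it is all randomised high-risk patients.
- **Time-to-event endpoints.** The list in SAP 2.9.2.4 has three entries: duration of response, of complete remission and of partial remission. Rescue is not among them.
- **Timing of rescue.** Protocol 10.4.1: "It is recommended that the patient is in the study for over one year". It may be given sooner where clinically warranted.
- **A parallel event.** SAP 3.2.1 and Protocol 14.1.7 analyse time from randomisation to the first open-label dose by Kaplan-Meier. Patients without that event are censored at the last date they were known to be on study.

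**The concern.** Non-responder imputation suits a favourable outcome such as remission. There, scoring a missing patient as a failure and scoring the event as not having happened are the same thing. For rescue therapy they are opposites. A failure would be a patient who was rescued; an event that did not happen means a patient who was not. The plan does not say which applies, so the choice falls to whoever programs the table.

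Either way, a patient who withdraws from the study before any rescue receives a value that nobody observed. The denominator also includes follow-up time in which rescue could not be seen. Because rescue is expected mainly after one year, early leavers miss most of the risk period.

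Withdrawal may also be related to the outcome. Protocol 8.3.2 lists starting a prohibited medication as a possible reason for withdrawal, and Protocol 10.4 prohibits other approved IgAN treatments. A patient who leaves for such a treatment could be tabulated as not rescued.

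At stake are the rescue rate in each arm, its exact interval and the CMH p-value, in two populations.

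**Working it through.** The documents give no rescue rate, withdrawal rate or power for this endpoint, so there is no planned figure to reproduce. What follows is an illustration.

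**Inputs from the documents:** follow-up of 96 weeks; 225 patients per arm (Protocol 14.1.2); two-sided 5% tests (Protocol 14.1.6).
**Assumed:** true rescue risk R, total withdrawal D, and independence of the two.

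**1. Withdrawn patients scored as not rescued.** Let withdrawal be uniform over 96 weeks and rescue risk be constant from Week 52 to Week 96. A rescue at week t is missed with probability D × t/96. The relative loss is therefore

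D × [(52 + 96)/2]/96 = D × 74/96 = 0.771 × D.

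| D | 10% | 15% | 20% | 25% |
|---|---|---|---|---|
| Relative loss | 7.7% | 11.6% | 15.4% | 19.3% |

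If rescue were spread evenly over Weeks 0 to 96, the factor would be 48/96 = 0.5, and the loss 5% to 12.5%.

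Take R = 20% in both arms, with D = 10% against 20%:
- 20% × (1 − 0.077) = 18.5%
- 20% × (1 − 0.154) = 16.9%

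The gap is about 1.5 points. Its standard error with 225 per arm is √[(0.185 × 0.815 + 0.169 × 0.831)/225] = 3.6 points, so the shift is under half a standard error.

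**2. Withdrawn patients scored as rescued.** The rate is 1 − (1 − R)(1 − D).

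| R in both arms | D = 10% | D = 20% | False difference |
|---|---|---|---|
| 20% | 1 − 0.8 × 0.9 = 28% | 1 − 0.8 × 0.8 = 36% | 8 points |
| 10% | 1 − 0.9 × 0.9 = 19% | 1 − 0.9 × 0.8 = 28% | 9 points |

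In the second row, an unstratified two-sided 5% test with 225 per arm would be significant about 61% of the time.

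**3. Check with a second model.** Let rescue and withdrawal times be exponential over T = 24 months, with hazards a = −ln(1 − R)/T and b = −ln(1 − D)/T. The not-rescued coding gives a/(a + b) × [1 − (1 − R)(1 − D)]. For R = 10% and D = 20%, this is 0.1054/(0.1054 + 0.2231) × 0.28 = 9.0%. Results for R = 10%:

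| D | Not rescued | Not rescued, rescue only after month 12 | Rescued |
|---|---|---|---|
| 5% | 9.8% | 9.6% | 14.5% |
| 10% | 9.5% | 9.2% | 19.0% |
| 20% | 9.0% | 8.5% | 28.0% |
| 30% | 8.4% | 7.7% | 37.0% |

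Kaplan-Meier with independent censoring targets 10% in every row. Over R from 5% to 20% and D from 5% to 30%, the not-rescued coding falls short by about 0.1 to 3 points, or up to 4.6 points if rescue starts only after month 12. The rescued coding is too high by about 4 to 29 points.

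**The case against.** The other side has a good deal to say.

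- **The imputation sentence never names rescue.** It reaches rescue because the endpoint is worded as yes or no, the rule covers all binary endpoints, and rescue is missing from the time-to-event list. That is an inference, but no passage offers another analysis. SAP 2.9.2.3.2 mentions time-to-event endpoints in general terms and does not name rescue either.
- **The not-rescued coding is ordinary crude incidence.** This stands. A reader might infer that both codings are equally wrong; the working shows that they are not. A reader might also infer that the sponsor intends the damaging one, but nothing in the documents says so.
- **The inputs are assumed.** This stands too. Rescue may be rare: Protocol 10.4.1 requires a doubling of UPE and a 30% fall in eGFR, each measured twice over eight weeks, and discourages rescue. Placing all risk after Week 52 enlarges the relative loss, since earlier rescue is permitted.
- **Loss of follow-up is limited.** Patients who only stop study drug keep attending visits (Protocol 8.3.1, 10.2.9), and rescued patients stay in follow-up. Patients who leave the study are asked to complete the Week 96 evaluations, which cover concomitant medication, unless consent is withdrawn. That visit finds earlier rescue but not later rescue. It would therefore be wrong to read every early stop as a missing outcome, or to say that the crude rate must be biased in both arms. That depends on an unknown withdrawal rate.
- **Kaplan-Meier has its own assumption.** Censoring must be non-informative, which withdrawal for prohibited medication may violate. The remedy has to address this.

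**Conclusion.** The point holds as a cheap improvement to a supportive analysis. A stated rule, applied as worded, puts response-endpoint imputation on an unfavourable event and leaves the direction of scoring open. If withdrawals are scored as not rescued, the understatement is modest. If they are scored as rescued, the rate is inflated heavily, and unequal withdrawal alone can produce a false difference of 8 to 9 points between arms. These sizes rest on assumed rescue and withdrawal rates and on independence between them.

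A reader might infer that the trial's main conclusions are at risk. The documents do not support that: SAP 2.9.1 places all endpoints other than the primary and key secondary outside type I error control and treats them as supportive.

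**What to change.** In SAP 2.9.2.4 and Protocol 14.1.10.3, exempt use of rescue therapy from non-responder imputation, and keep that rule for the remission and percent-reduction endpoints. Then specify, for both populations:

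1. Time from randomisation to first rescue therapy by Kaplan-Meier, censored at the last date known on study, matching SAP 3.2.1.
2. The Week 96 cumulative incidence by arm, with a log-rank test stratified by randomisation strata. SAP 2.9.2.3.2 plans a stratified log-rank test and SAP 2.9.2.4 a stratified Cox model, so name the one that applies here.
3. How death is handled.
4. A sensitivity analysis that counts withdrawal for a prohibited IgAN medication as an event, because that censoring may be informative.

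The observed count of rescued patients can still be shown. If the crude rate is retained, the SAP should at least state how withdrawn patients without recorded rescue are classified.

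The cost is a few sentences and a few extra tables. Protocol 14.1.4 requires a protocol amendment only when a principal feature changes, so this can go into the SAP before the interim snapshot, with the protocol text aligned. The headline rate will change: slightly higher than under the not-rescued coding, lower than under the rescued coding.

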## 2.3. Estimand Framework for the Primary and Key Secondary Endpoints

Care is needed when selecting an estimand since the ICH E9 Estimand Addendum unfortunately promotes analyses that do not respect the randomization, such as ‘theoretical’ and ‘while on

treatment' estimands, and, thus, are likely to be heavily biased. The principal estimands chosen for the primary and key secondary efficacy endpoints outlined in [Table 1](#) avoid such bias by respecting the randomization.

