The following time-to-event endpoints will be analyzed by the KM method for each treatment group for the FAS population. If calculable, median time with 95% CI will be provided by treatment group. The HR, CI and p-value will be estimated via Cox regression analysis stratified for the randomization strata and with treatment as the sole class factor.

- Duration of treatment response will include patients in the FAS population who achieve  $\geq 30\%$  reduction from baseline in 24-hour UPE only. Patients who respond but do not relapse during the study will be censored at their last date of 24-hour UPE
- Duration of complete proteinuria remission will include patients in the FAS population who achieve 24-hour UPE  $< 0.3$  g/day only. Patients who achieve complete proteinuria remission but whose 24-hour UPE does not increase to  $\geq 0.3$  g/day during study will be censored at the last date of 24-hour UPE
- Duration of partial proteinuria remission will include patients in the FAS population who achieve 24-hour UPE  $< 1$  g/day only. Patients who achieve partial proteinuria remission but whose 24-hour UPE does not increase to  $> 1$  g/day during study will be censored at the last date of 24-hour UPE

Change from baseline in RBC/HPF will be summarized descriptively by treatment group and scheduled visit.

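### Exploratory durations of response and remission are compared between arms only in patients who responded, so their hazard ratios and p-values are not randomised comparisons

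*SAP*

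**What the plan says.** SAP 2.2 makes the Full Analysis Set the efficacy population, "defined as all randomized patients in the high-risk proteinuria group"; for the all-patients population it is everyone randomised. SAP 2.9.2.4 names that set for all other efficacy endpoints and then narrows it for the three durations:

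- "Duration of treatment response will include patients in the FAS population who achieve" a UPE reduction of at least 30%, and no other patients;
- "Duration of complete proteinuria remission will include patients in the FAS population who achieve 24-hour UPE" below 0.3 g/day, and no other patients;
- "Duration of partial proteinuria remission will include patients in the FAS population who achieve 24-hour UPE" below 1 g/day, and no other patients.

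Arms are compared by Kaplan-Meier medians and then: "The HR, CI and p-value will be estimated via Cox regression analysis stratified for the randomization strata", "and with treatment as the sole class factor". No caveat about the selected set is given.

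Protocol 14.1.10.3 has a general sentence for time-to-event endpoints: "Log-rank test stratified by the randomization stratum will be performed". SAP 2.9.2.3.2 has an equivalent sentence. Neither states the responder restriction. Both inherit it for these endpoints, because duration of response is counted from the first qualifying response (Protocol 7.2.5, SAP 2.1).

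The three endpoints are listed as exploratory in Protocol 7.2.5 and SAP 2.1. Protocol 14.1.6.3 and SAP 2.9.1 treat all tests outside the primary and two key secondary endpoints as supportive, without type I error control.

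**The concern.** Randomisation makes the arms comparable as randomised. It does not make the responders in one arm comparable with the responders in the other. If narsoplimab lowers proteinuria, its responders include patients who would not have responded on placebo, and these may be more or less prone to relapse than patients who respond either way. A responder-only hazard ratio mixes that difference in composition with any true effect on durability, and the data cannot separate them. Stratifying on baseline eGFR and UPE category balances only those two factors.

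What is at stake is interpretation. Study drug is given in short courses with retreatment on relapse (Protocol 7.1), so a hazard ratio and p-value for duration of response are likely to be quoted. The composition effect can run either way. A drug that brings harder-to-treat patients into response may look as if its responses are shorter.

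**Working it through.** The documents give no event count, power or hazard ratio for these endpoints, so there is no planned figure to reproduce.

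**Inputs from the documents.** Log-scale effect -0.393 and SD 0.80 for change in UPE (Protocol 14.1.1, SAP 1.3.1); 1:1 allocation; planned sizes 180, 280 and 450; two-sided 5% tests; last visit at Week 96.

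**Assumptions.** Placebo mean log change 0; response at Week 12, leaving 96 - 12 = 84 weeks of follow-up; exponential relapse times with a median of 48 weeks in patients who would respond on either arm.

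**Step 1: who responds.** P(response) = Φ((ln 0.70 - mean)/SD), with ln 0.70 = -0.357.

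- Placebo: Φ(-0.357/0.80) = Φ(-0.446) = 32.8%.
- Narsoplimab: Φ((-0.357 + 0.393)/0.80) = Φ(0.045) = 51.8%.
- Added share of narsoplimab responders: (51.8 - 32.8)/51.8 = 37%.

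With 140 per arm that is about 46 placebo and 73 narsoplimab responders, some 27 of the latter without a placebo counterpart. The added share runs from 32% to 55% over SD 0.63 to 0.80, placebo mean -0.2 to +0.2, and effect -0.393 or -0.431. The last is ln 0.65, the exact log of a 35% reduction; with SD 0.80 and placebo mean 0 it gives 32.8% and 53.7%. This is a one-visit calculation. Counting a response at any visit, as the definition does, raises both fractions and would probably make the added share smaller.

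**Step 2: hazard ratio when the drug changes no common responder's relapse.** Let the added responders relapse at r times the hazard of the others. At the start of follow-up the expected ratio is 0.633 + 0.367r: 1.37 for r = 2, 1.73 for r = 3, 0.82 for r = 1/2 and 0.76 for r = 1/3. Fast relapsers leave the risk set first, so the ratio then falls. A Cox fit averages over that decline.

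**Step 3: simulation.** Unstratified Cox model in responders, treatment as the only factor, 4,000 trials per cell. Nominal error is 2.5% in each direction.

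| r | HR, N = 280 | False result, N = 180 / 280 / 450 |
|---|---|---|
| 3 | 1.41 | harm 23% / 34% / 51% |
| 2 | 1.28 | harm 12% / 19% / 29% |
| 1 | 1.00 | 4.4% to 4.9% in total |
| 1/2 | 0.78 | benefit 12% / 19% / 26% |
| 1/3 | 0.70 | benefit 23% / 33% / 49% |

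A second run at N = 280 gave hazard ratios of 1.28 to 1.40 with false harm in 18% to 34%, so the rates are good to about a percentage point. With a median duration of 24 or 96 weeks instead of 48, N = 280 gives 1.24 to 1.53 for r = 2 to 3, and 0.76 to 0.80 for r = 1/2.

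**Step 4: an all-randomised alternative.** Weeks in response to Week 96, with 0 for never-responders, compared in everyone (5,000 trials per setting, no dropout, unadjusted). With no drug effect, rejection was 4.7%, 5.4% and 4.8% at N = 180, 280 and 450. When narsoplimab only added responders, the mean difference was +4.2 to +13.2 weeks, and a false finding of shorter response occurred in at most 0.2% of trials.

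**The case against.** The strongest reply is that little hangs on these tests. The endpoints are exploratory and supportive. Durability is a secondary objective (Protocol 6.2, SAP 1.1), but the plan evaluates it by time-averaged change in log UPE over Weeks 36 to 48 and 36 to 72 in the Full Analysis Set. That analysis uses multiple imputation and the randomisation strata and excludes only on-study patients who have not reached Week 36. Response and remission rates are also compared in the full set, with non-responder imputation. All of this stands and limits the importance of the point. It does not rescue the hazard ratio, because supportive status deals with multiplicity and not with selection.

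A reader might infer that the main durability assessment is compromised. It is not: time-averaged UPE does not condition on response.

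A reader might also infer that a constant, non-waning UPE reduction would produce a spurious benefit. In simulations of a constant 35% reduction (140 per arm, assumed within-patient log SD 0.2 to 0.3) the responder-only hazard ratio was 0.79 to 0.81. In simulated patients who would respond on either arm it was 0.70 to 0.74. Relapse as defined requires UPE above 1 g, so a lower level truly makes relapse less likely. There the restriction weakens a real effect and does not invent one.

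A reader might take SAP 2.3 as forbidding the analysis. Its warning about "analyses that do not respect the randomization" supports the reasoning, but that section justifies the estimands for the primary and key secondary endpoints and sets no rule for exploratory summaries.

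Finally, weeks in response with zeros for non-responders is not pure durability. Step 4 confirms this: it moves when only the response rate changes. It needs that label.

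**Conclusion.** The point holds for the three exploratory duration endpoints. Their hazard ratios, intervals and p-values compare groups formed after randomisation and have no valid randomised interpretation. At N = 280, relapse hazards in the added responders that differ two- to three-fold from the rest move the hazard ratio to about 1.28 to 1.40, or to 0.70 to 0.78. The false significant results are then about 18% to 34% and 19% to 33%, against a nominal 2.5% in each direction.

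These sizes rest on the assumed relapse hazards, the placebo mean of 0 and response at one visit. The direction cannot be known beforehand. Bias needs both a difference in response between arms and a different relapse risk in the added responders; if the risks are equal, the test holds its level. Primary and key secondary conclusions do not change. Priority is minor to moderate: worth correcting because it is cheap, and not a threat to the trial's main inference.

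**What to change.** In SAP 2.9.2.4, keep the responder-only Kaplan-Meier curves and medians with their intervals, labelled as description. Delete the hazard ratio, its confidence interval and the p-value for the three durations. Exempt the same endpoints from the log-rank sentences in SAP 2.9.2.3.2 and Protocol 14.1.10.3; otherwise a between-arm test remains.

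If a between-arm comparison is wanted, compare all patients in the Full Analysis Set on weeks in response (and in partial and complete remission) up to Week 96. Count 0 for never-responders, adjust for the randomisation strata, and state a rule for patients lost before Week 96. Describe the result as combining response rate and durability, and show the descriptive curves beside it.

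The same SAP paragraph sets the partial-remission cut-off at 1 g/day, while SAP 2.1 and Protocol 7.2.5 use 0.6 g/day. These should be reconciled in the same edit.

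The cost is a paragraph in SAP 2.9.2.4 and a sentence in each of the other two sections. No new data are needed. What is lost is a single number meant to isolate durability, which the responder-only model could not supply.
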